	
The variables for the secondary objective are:
 
Laboratory parameters (including date of test), if collected in routine clinical practice at the physician’s discretion:
 
 • Biochemistry parameters: 
 ○ Sodium, potassium, albumin, creatinine, bilirubin, aspartate aminotransferase (AST), alanine aminotransferase (ALT), gamma-glutamyl transferase (GGT), alkaline phosphatase, C-reactive protein (CRP), urea, estimated glomerular filtration rate (eGFR). • Urinalysis parameters: 
 ○ Urine albumin/creatinine ratio and spot urine dipstick test. • PEG plasma levels 
Parameters for neurological assessments to be documented if available include the following:
 
 • Date of assessment • Level of consciousness, cranial nerves, body tone, strength (of the four extremities), reflexes, sensory aspects, gait, coordination and fine motor function, mental state. • For children: evaluation of appearance, language, social interaction.

Data sources
	
Historical data based on medical records or on information provided by the patient during routine clinical visits. Treatment-related data documented during visits that take place in routine practice.

Study size
	
The study aims to observe 50 patients for at least 4 years each. Assuming a dropout rate of approximately 20% (due to lost to follow-up cases or withdrawals), 60 patients will be enrolled.

Data analysis
	
Statistical analyses will be of an explorative and descriptive nature. The study is not aimed to confirm or reject predefined hypotheses; hence no formal hypothesis testing will be performed.
 
All variables will be analyzed descriptively with appropriate statistical methods: categorical variables by frequency tables (absolute and relative frequencies) and continuous variables by sample statistics (i.e., mean, standard deviation [SD], minimum, median, quartiles, and maximum). Continuous

	variables will be described by absolute value and as change from baseline per analysis time point, if applicable.
Milestones	First patient first visit: Q2 2020 Last patient first visit: planned Q2 2023 Last patient last visit: planned Q2 2028 Final report: planned Q4 2028

5. Amendments

None.

6. Milestones

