7.1 Epidemiology, classification, and treatment of hemophilia A

Hemophilia A is an X-linked, inherited, genetic bleeding disorder characterized by the deficiency of clotting factor VIII (FVIII) [1],[2]. Hemophilia A comprises approximately 80% of all hemophilia cases, with an annual incidence of approximately 1 in 5,000 live male births [1],[2]. All races and economic groups are affected equally [2]. Prevalence estimates vary by country, ranging between 5 and 21 cases per 100,000 male births. According to the World Federation of Hemophilia, it is estimated that only between 25% and 30% of hemophilia patients globally are adequately diagnosed and managed [3]. Furthermore, up to 75% of hemophilia patients globally live in developing countries in which access to specialist health care professionals and modern therapies prove to be a substantial barrier.

Normal FVIII levels vary between 50% and 150%. The severity of hemophilia A is classified by the amount of clotting factor present in the blood: mild, if the patient has >5% normal clotting factor (>0.05 international units [IU]/mL); moderate, if the patient has between 1% and 5% (≥ 0.01 to 0.05 IU/mL) normal clotting factor; and severe, if the patient has <1% (<0.01 IU/mL) normal clotting factor. Patients with mild or moderate hemophilia A typically have bleeds only following trauma and tend to report fewer major health-related quality of life impacts. It is estimated that between 60% and 70% of patients with hemophilia A have the severe form of the disease [4]. For these patients, bleeding events often spontaneously occur in joints or muscles or with minimal or unknown trauma to the affected area [5]. Recurrent bleeding in the joints can lead to progressive joint damage, loss of joint mobility, and chronic pain.

The two main approaches to treatment are on-demand therapy, in which the patient is treated in response to a bleed, or prophylactically, in which the patient is treated regularly to prevent bleeding episodes. Prophylaxis is now considered the standard of care in many countries, especially in the pediatric and adolescent population, as it has been shown to reduce complications from repeated bleeds, particularly joint arthropathy [1].

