9.1 Study design

This is a multinational, open-label, prospective, non-interventional, multicenter, cohort study of PTPs with hemophilia A receiving damoctocog alfa pegol as prophylaxis treatment. The study is planned to be conducted in multiple countries in Europe.

At study start, retrospective data will be collected on the patients' baseline characteristics (including genotyping [where available], medical condition and hemophilia treatment history). Also at study start and then at each physician visit during the follow-up phase, data will be recorded on regimens used, AEs of special interest including hypersensitivity reactions, loss of drug effect, renal impairment, neurocognitive disorders, inhibitor development, other AEs, SAEs and drug-related ARs in standard clinical practice. If collected in routine clinical practice at the physician's discretion, parameters relating to kidney and liver function (e.g. creatinine, estimated glomerular filtration rate (eGFR), alanine transaminase (ALT), aspartate aminotransferase (AST), bilirubin), PEG-plasma level and abnormal findings from neurological assessments will be captured in the eCRF/EDC system. Adverse reactions (ARs) relating to the system organ classes of the nervous system and psychiatric disorders will be recorded.

Patients/legal representatives and physicians can choose from different prophylaxis regimens with damoctocog alfa pegol following approved local labels or any other regimen prescribed by the physician as part of normal clinical practice. Patients/legal representatives and physicians can choose to change the dosing regimen based on the patient's response to treatment at any time. A reason for the dose and/or frequency change should be documented.

The planned observation period for each of at least 50 patients will be a minimum of 48 months for the collection of long-term safety data and the prospective monitoring of clinical effects of long-term exposure of prophylaxis with damoctocog alfa pegol in PTPs with hemophilia A.

Due to the observational nature of the study, follow-up visits cannot be scheduled specifically for study purposes and it is unknown when a patient will come for the next visit. Thus, data collection will occur continuously throughout the patient's observational period (i.e., each visit or assessment

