9.1.2 Secondary endpoints

The secondary endpoints are:

- Number of ARs that are defined within the system organ classes nervous system and psychiatric disorders from study start to end of the study
- Number of ARs related to hepatic or renal function from study start to the end of the study
- Change in kidney and liver function parameters from study start to the end of the study
- Change in PEG-plasma levels from study start to the end of the study
- Number of patients with abnormal findings as assessed by neurological examination across all age groups from study start to the end of the study

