9.3 Variables

The physician collects historical study-relevant data (demographic and clinical characteristics) from medical records if available (or by interviewing the patient at the initial [baseline] visit) and treatment-related data during visits (see section 9.2.5). In this non-interventional study, the visits are not scheduled by the study team (i.e. visits occur at the physicians' discretion and independent of the

⁶ Events up to 30 days after the last dose of damoctocog alfa pegol within the study period.

⁷ Including duration, treatment, seriousness and outcome.

⁸ Sodium, potassium, albumin, creatinine, bilirubin, aspartate aminotransferase (AST), alanine aminotransferase (ALT), gamma-glutamyl transferase (GGT), alkaline phosphatase, C-reactive protein (CRP), urea, estimated glomerular filtration rate (eGFR).

⁹ Urine albumin/creatinine ratio, spot urine dipstick test.

¹⁰ Including (for all ages) level of consciousness, cranial nerves, body tone, strength (of the four extremities), reflexes, sensory aspects, gait and coordination and fine motor function. In the case of children, evaluation of appearance, language, social interaction. In the case of adults, mental state.

patients' participation in the study. It is assumed that at most Hemophilia treatment centers; patient visit frequency is at least 1-2 times per year). The physician documents the study-relevant data for each patient in the eCRF/EDC system. The pCRF (paper version of the eCRF) is kept as a stand-alone document (see [Table 3](#)) and is available upon request.

This is a non-interventional study and the clinical decisions of the physicians must not be affected by study participation. As such, data on many of the secondary endpoints (e.g. PEG-plasma, eGFR, ALT) may not be available for all patients. Nevertheless, if they were collected in local routine clinical practice at the investigator's discretion, all results will be documented in the eCRF/EDC system. In the case that an investigator wants to determine the PEG levels in plasma, e.g. in case of any AE which could be related to PEG accumulation, one or more laboratories will be appointed and kits will be provided to the sites for sampling as per the investigator's discretion. Bayer Consumer Care AG will offer support for the procedure if requested.

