9.7.4 Analysis of secondary variables

Laboratory parameters will be analyzed descriptively. Results will be displayed by summary statistics and as change from baseline.

A descriptive analysis will be performed for the number of patients with laboratory parameters outside of the normal ranges.

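### The secondary neurological endpoint counts any abnormal finding without comparing it with the initial visit, so deficits present at entry are mixed with those arising in follow-up

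*Protocol*

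**What the plan says.** Protocol 9.1.2 lists the neurological endpoint as "Number of patients with abnormal findings as assessed by neurological examination across all age groups from study start to the end of the study". The kidney and liver item in the same list is worded differently: "Change in kidney and liver function parameters from study start to the end of the study". The PEG plasma item is also a change.

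Section 9.7.4 covers laboratory parameters only. It says "Results will be displayed by summary statistics and as change from baseline", and then adds "A descriptive analysis will be performed for the number of patients with laboratory parameters outside of the normal ranges". It gives no analysis for the neurological endpoint. The general rule in the Abstract and in 9.7.1 is that continuous "variables will be described by absolute value and as change from baseline per analysis time point, if applicable"; categorical variables get frequency tables.

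Table 2 marks the neurological assessment for the initial visit and for follow-up visits, if available in routine practice. Section 9.3.2 lists the items examined, among them strength of the four extremities, reflexes, sensory aspects, gait and coordination.

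On what is recorded, 9.1 says that "abnormal findings from neurological assessments will be captured in the eCRF/EDC system", whereas 9.3 says of data on the secondary endpoints that, if they were collected, "all results will be documented in the eCRF/EDC system".

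**The concern.** Section 9.2.5 makes the initial visit the start of the observation period, so a deficit found at that visit falls inside the period over which the endpoint counts. Such deficits can be expected in this population. Section 7.1 states: "Recurrent bleeding in the joints can lead to progressive joint damage, loss of joint mobility, and chronic pain". Several of the examined items can be abnormal for that reason alone. Apart from mental incapacity or other barriers to understanding or cooperation, no exclusion criterion in 9.2.1.2 removes patients with existing joint or neurological deficits.

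The secondary objective in 8.2 is to monitor the effects of long-term exposure, including on neurological function. A count that pools long-standing deficits with those arising in follow-up does not answer that question. With no comparator group, the background cannot be subtracted afterwards. A reader of the final report could take background disease for a signal, or could dismiss a real change as background.

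**Working it through.** **Is there a baseline condition anywhere?**

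- 9.1.2, neurological item: a count of patients with abnormal findings; nothing about new, worsened or baseline.
- 9.1.2, kidney and liver parameters and PEG levels: each a change from study start.
- Abstract and 9.7.1: change from baseline for continuous variables only. A yes/no finding is categorical and gets a frequency table.
- 9.7.4: laboratory parameters only.
- Table 2: an initial-visit assessment is foreseen, if available, but no analysis text uses it for this endpoint.

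So the protocol contains no rule that separates findings at entry from later ones for the neurological endpoint. For the laboratory parameters it does; only the added out-of-range count lacks one.

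**The plan's own figure.** Section 9.5 states a 64% chance of at least one event among 50 patients at a risk of 2%. Check: 1 − (1 − 0.02)^50 = 1 − 0.364 = 0.636. The figure is reproduced.

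**Illustration of the mixing.** Inputs: n = 50 assessed patients (the target in 9.5); new-onset risk i = 2% (the risk 9.5 uses in general, not an estimate for neurological findings); share abnormal at entry b = 5% to 30% (an assumption, since the protocol gives none).

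- Abnormal at entry: 50 × b
- Newly abnormal: 50 × (1 − b) × i
- Counted as worded: the sum of the two
- Share already abnormal at entry: b / [b + (1 − b) × i]

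| b | At entry | New (i = 2%) | Counted | Share at entry |
|---|---|---|---|---|
| 5% | 2.5 | 0.95 | 3.45 | 72% |
| 10% | 5.0 | 0.90 | 5.90 | 85% |
| 20% | 10.0 | 0.80 | 10.80 | 93% |
| 30% | 15.0 | 0.70 | 15.70 | 96% |

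With i = 5% the shares are 51%, 69%, 83% and 90%. The share does not depend on n, so it would be the same with fewer patients assessed, provided b and i apply to those assessed.

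**What a new-onset count can show.** Among patients normal at entry (48, 45, 40 and 35 of 50, rounded), the chance of at least one newly abnormal patient at 2% is 1 − 0.98^48 = 62%, then 60%, 55% and 51%. The 64% of 9.5 would apply only if all 50 were normal at entry.

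**The case against.** The strongest reply is that new onset is already captured elsewhere. Section 11.1 counts a new illness, or the worsening of a concomitant one, as an adverse event. Section 11.2 treats events before the first on-study dose as medical history. Section 9.9 says clinically relevant changes in organ function and new symptoms would be documented as adverse events. Neurocognitive disorders are of special interest and are analysed separately. This stands. A reader might infer that a true neurological effect would be buried, or that the primary endpoint is contaminated; the protocol supports neither. The reply does not change what the examination endpoint itself counts.

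A reader might also infer that the kidney and liver endpoint has the same fault. It does not: it is defined as a change and analysed against baseline. A patient with chronically raised ALT is not an endpoint case at the first visit. Only the supplementary out-of-range count, which is not a listed endpoint, would include that patient.

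A third tempting inference is that normal examinations leave no record. Section 9.1 names abnormal findings but does not restrict capture to them. Sections 9.3 and 9.3.2, Table 2 and the quality review in 9.8.2 all point to recording everything available. The sentence in 9.1 needs aligning; it does not prove that data are lost.

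Finally, the analysis plan may well contain shift tables, since 9.7.1 leaves table content to it. That is fair for layout. The endpoint definition, however, is fixed in the protocol, and an analysis plan finalised before the first database lock could not recover normal results that a site had not entered.

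**Conclusion.** The point holds for the neurological endpoint. As defined, it mixes deficits present at entry with those arising in follow-up, and no other protocol text separates them. It is a secondary, descriptive endpoint and the primary adverse event analysis is unaffected, so this is a correction that should be made rather than a threat to the study.

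The size cannot be established from the protocol. The range of 72% to 96% rests on an assumed 5% to 30% abnormal at entry and a borrowed 2% risk; at a 5% risk the lower end is 51%. Over these ranges, half or more of the patients counted would have been abnormal at entry.

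One limit applies to the remedy as well. Section 9.2.4 admits patients already receiving the product, so a finding at entry is not necessarily a finding before exposure. Patients abnormal at entry must therefore stay visible rather than be removed.

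**What to change.** In 9.1.2, define the endpoint as the number of patients with a new or worsened neurological finding compared with the initial-visit assessment. In 9.7.4, add its analysis:

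- give the numbers assessed at entry and at follow-up as the denominator;
- show patients abnormal at entry in a separate row, split by prior damoctocog alfa pegol exposure (Table 2 already collects that history);
- show patients with no entry assessment in another row;
- present the out-of-range laboratory count by baseline status, as a shift table. The kidney and liver endpoint itself needs no change.

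In 9.1, reword the capture sentence so that every neurological assessment performed is recorded, whether normal or abnormal, in line with 9.3, 9.3.2 and Table 2.

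The cost is protocol wording, a normal/abnormal entry for each examination if the eCRF lacks one, and a few table rows. No extra visit or test is needed. The downside is that patients without an entry assessment drop out of the new-onset count. Because the assessment depends on routine practice, that group may be sizeable, which is why it needs its own row.

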9.2 Setting

9.2.1 Eligibility

All PTPs with hemophilia A receiving prophylaxis damoctocog alfa pegol will be eligible to be enrolled into the study. The confirmation of eligibility criteria for patients enrolled or reasons for non-enrollment will be collected in the eCRF/EDC system (see section 9.2.4). The rationale for restricting the study population to patients on prophylaxis treatment is that these patients may have a higher treatment exposure as compared to 'on-demand' patients. Otherwise, indications according to the local market authorization should be carefully considered.

9.2.1.1 Inclusion criteria

- Signed informed consent/assent will be obtained before any study-related activities (i.e. any procedure related to the recording of data according to the protocol)
- PTPs with hemophilia A assigned to Jivi prophylaxis treatment
- Negative FVIII inhibitor test before study entry

² AEs including, but not limited to, hypersensitivity reactions, loss of drug effect, renal impairment, neurocognitive disorders and inhibitor development.

- Decision to initiate treatment with commercially available Jivi has been made by the treating physician before and independently from the decision to include the patient in this study

9.2.1.2 Exclusion criteria

- Known or suspected contraindications to Jivi or related products
- Mental incapacity, unwillingness or other barriers precluding adequate understanding or cooperation
- Participation in an investigational program with interventions outside of routine clinical practice

9.2.2 Withdrawal

In this observational study, withdrawal from the study is independent of the underlying therapy and will not affect the patient's medical care. Each patient may withdraw from the study at any time and without giving a reason. If a patient/legal representative (in case of minors) wants to terminate study participation, no further data will be collected. In case a patient/legal representative would like to withdraw the consent given earlier, s/he should inform his/her doctor and the site should document the withdrawal in the electronic Case Report Form (eCRF) as well as in the patient medical records.

9.2.3 Replacement

Enrollment will stop as outlined in the milestones or when the target sample size is reached. Patients who drop out after the end of enrollment (e.g. withdrawal, lost to follow-up) will be replaced to ensure that all in all 50 patients have reached a minimum follow-up of 4 years.

9.2.4 Representativeness

The eligibility criteria have been selected to allow for a broad representation of patients within the study. The study will enroll previously treated hemophilia A patients initiating or currently receiving prophylaxis damoctocog alfa pegol. Prophylaxis therapy is the recommended standard of care for patients with severe disease and those with moderate disease with a severe patient bleeding profile. By enrolling all eligible patients with mild, moderate or severe disease consecutively, the study will capture real-world data.

Previously untreated hemophilia A patients are not eligible for this study as the safety of damoctocog alfa pegol in this patient population has not been established. Given the incidence rate of hemophilia A, 1 in 5,000 live male births, previously untreated patients represent approximately 2% of the hemophilia patient population. Thus, the study population is broadly representative of mild, moderate, and severe hemophilia A patients, even when previously untreated patients are excluded.

In addition, the inclusion of a representative sample of study sites (i.e., health care providers, hospitals, etc.) in terms of geography, practice size, and academic or private practice type is aimed as a measure to enhance the generalizability of study results. Nevertheless, the final sample of study sites will strongly depend on the willingness of physicians to participate in the study.

The patients documented in the study should be selected based only on eligibility according to a minimal set of selection criteria (see sections 9.2.1.1 and 9.2.1.2). No further selection should be

applied, thus increasing the generalizability of the study results. Physicians will be asked to sample consecutive patients whenever possible. This consecutive sampling approach is intended to reduce selection bias by the treating physicians in relation to which patients they enroll in the study, especially with regard to factors that may be associated to the outcome or prognosis of those patients (e.g., demographic characteristics, multiple co-morbidities, as well as concomitant medications), thus maintaining the observational character and enhancing the external validity of the study. Furthermore, an anonymous patient log file (integrated into the Electronic Data Capture [EDC] system) will be used by each site to document patients not enrolled in the study (without recording patient-specific data), including the reason for not enrolling (e.g., refused consent, eligibility criteria not met, etc.).

